9.7.3. Safety Analyses

Several analyses corresponding to the comparative cohort and SCRI designs will be conducted to assess whether there is an increased risk of outcomes associated with ABRYSVO vaccination. Analyses will be conducted among all individuals meeting the study eligibility criteria.

- Incidence rates of prespecified outcomes among the vaccinated cohort will be compared to rates observed in the unvaccinated cohort.
- Self-controls: Among individuals who experienced prespecified outcomes following vaccination, the SCRI design will be used to compare the incidence of outcomes in the risk interval following vaccination to the incidence in the post-vaccination control interval in the same individual.

9.7.3.1. Comparison with Unvaccinated Cohort

For each of the immunocompromised, renally impaired or hepatically impaired populations respectively, the incidence rates of the prespecified outcomes following administration of ABRYSVO will be compared against the incidence rates of the prespecified outcomes among individuals who did not receive ABRYSVO or any other vaccine at index.

An ATT weighting will be used to ensure baseline comparability between the ABRYSVO vaccinated cohort and unvaccinated cohort. ATT weighting creates a "pseudo-population" in which the distribution of covariates is, on average, the same in each cohort.⁵⁷ Specifically, ATT weights will be calculated to allow for estimation of the average treatment effect among individuals receiving ABRYSVO.⁵⁷ This approach will be taken to ensure that inference from the analysis will be applicable to the vaccinated population. Individuals receiving ABRYSVO will receive an ATT weight of one. Individuals not receiving ABRYSVO will receive an ATT weight equal to the odds of receiving ABRYSVO conditional on their demographic and clinical characteristics as of the index date, which will be calculated based

PFIZER CONFIDENTIAL CT24-WI-GL02-RF02 5.0 Non-Interventional Study Protocol Template For Secondary Data Collection Study 01-Aug-2023 Page 46 of 72 on the PS. The PS is defined as an individual's probability of receiving ABRYSVO, conditional on observed baseline covariates, and will be calculated using a logistic regression model. To select the variables to be included in the PS logistic model, a systematic approach based on clinical relevance, prior research, and statistical criteria will be used. The PS logistic regression model may include the cohort variable (i.e, ABRYSVO versus unvaccinated control) as the dependent variable, the independent variables that are deemed clinically important and have shown good control of confounding for previous comparative vaccine studies (e.g., age, sex, place of residence, co-morbidity indices, socioeconomic status/education level),⁵⁸ and baseline covariates that have crude standardized differences $\geq 10\%$ between the two cohorts. Specifically, ATT weights will be PS/(1-PS) for individuals with no record of ABRYSVO. The distribution of weights will be examined to assess extreme values, and truncation will be considered if necessary.

Individuals will be followed from the index date until death, end of administrative follow up (and/or risk interval), end of the study period, or the date of ABRYSVO/RSV vaccination (for unvaccinated individuals who later receive any RSV vaccine only), whichever occurs first. The degree of loss to follow-up will be examined. If the censoring rates differ by exposure group (i.e, indicating informative censoring) and high censoring rates (e.g., >20%) are observed, IPCW will be derived to account for informative censoring, where the weight will be calculated for each individual as the inverse of the probability of remaining uncensored during the risk interval. The stabilized IPCW will be calculated as follows, where A= vaccination, V = covariates to adjust, and C=0 represents that the patient has remained uncensored: (Pr[C=0 | A=1])/(Pr[C=0 | A=1,V=v]) for the vaccinated cohort; (Pr[C=0 | A=0])/(Pr[C=0 | A=0,V=v]) for the unvaccinated cohort.

The final weights will be calculated as the product of the ATT weight and IPCW (ATT x IPCW) if informative censoring is observed, and the ATT weight will be used as the final weight if informative censoring is not observed. The distribution of final weights (e.g., mean, SD, minimum, and maximum values) will be examined and extreme weights will be truncated or capped at the 1st and 99th percentile. After weighting, the distribution of baseline characteristics will be evaluated between the vaccinated cohort and the unvaccinated cohort, and variables that remain inadequately balanced (standardized difference >10%) between the two cohorts will be included as regression model covariates in a doubly robust approach.

Weighted Poisson regression models will be conducted to calculate IRRs of outcomes among vaccinated cohort vs. unvaccinated cohort. Incidence rate ratios will be summarized, and robust variance estimators will be used to calculate the corresponding 95% CIs.

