9.7.2. Incidence Rates of Outcomes

Incidence rates per 1,000 patient-years (and corresponding 95% CIs) will be calculated for prespecified outcomes (as described in Section 9.3.2) as the total number of incident events divided by the total observation time/person-time. The number of cases and incidence rates of each outcome will be reported for each of the populations of interest (i.e, immunocompromised, renally impaired, and hepatically impaired populations separately) in the vaccinated and unvaccinated cohorts.

For outcomes with unknown risk windows or those that require longer follow-up (e.g., death), the cumulative incidence will be computed, which will be estimated with a 1 - Kaplan-Meier survival curve, as well as with adjusted parametric incidence curves.⁵⁶ Time to outcome onset will be defined as the time from the index date until the occurrence of the prespecified outcome event or censoring. For most outcomes, the associated severity and rapidity of onset are likely to result in a healthcare encounter close to the time of outcome onset, so the date of onset will be assumed to be the date of the healthcare encounter. The SAP will elaborate on further analyses for outcomes that may have a time lag between symptom onset and a healthcare encounter (e.g., DVT, diabetes type 1).

For individuals without an outcome, the censoring date will be defined as the date of death, date of RSV vaccination (for unvaccinated individuals who later receive any RSV vaccine only), end of the administrative follow up, or the end of data availability, whichever occurs earliest. For outcomes with defined risk windows, censoring will also occur at the end of the risk window. For composite outcomes, follow-up will be censored at the date of the first occurrence of any of its components.

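### The censoring weight is one full-interval weight per person applied to partial follow-up, so when it is used it over-corrects and reverses the sign of the censoring bias

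*Protocol*

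**What the plan says.** Protocol section 9.7.3.1 follows each person until death, end of administrative follow-up or of the risk interval, end of study, or, for comparators, "the date of ABRYSVO/RSV vaccination (for unvaccinated individuals who later receive any RSV vaccine only"). If censoring differs between cohorts and "high censoring rates (e.g., >20%) are observed", censoring weights are derived: "the weight will be calculated for each individual as the inverse of the probability of remaining uncensored during the risk interval". The stabilised formula is Pr[C=0 | A] / Pr[C=0 | A, V], "where A= vaccination, V = covariates to adjust, and C=0 represents that the patient has remained uncensored". It has no time index.

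The same section continues: "The final weights will be calculated as the product of the ATT weight and IPCW (ATT x IPCW") when informative censoring is seen. These weights are capped at the 1st and 99th percentiles. Covariates still more than 10% out of balance after weighting enter the regression. Then: "Weighted Poisson regression models will be conducted to calculate IRRs of outcomes among vaccinated cohort vs. unvaccinated cohort".

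Section 9.7.2 computes a rate as "the total number of incident events divided by the total observation time/person-time". For people without an outcome, "the censoring date will be defined as the date of death, date of RSV vaccination", the end of administrative follow-up or the end of data availability, whichever is earliest. Neither section splits follow-up into intervals or gives censored people zero weight.

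**The concern.** Censoring at later RSV vaccination affects comparators only, so it is built into the design. Inverse probability of censoring weighting is the correction the protocol states for it. The trigger of about 20% censoring is most plausible for outcomes followed for 365 days: type 1 diabetes, narcolepsy, arrhythmia, coronary artery disease, heart failure, microangiopathy, stress cardiomyopathy, acute respiratory distress syndrome and death. Table 1 assigns these to the cohort design alone, so apart from a possible SCRI for atrial fibrillation and supraventricular arrhythmias (section 9.7.4) no within-person analysis cross-checks them.

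A person censored on day 100 contributes 100 days. Under the stated formula those days carry the inverse probability of reaching the end of the interval, although everyone like that person was more likely than that to be under observation on each of them. Covariate groups that leave often are then weighted up too far, and the baseline balance produced by the ATT weights is disturbed. In a safety study a distorted rate ratio can create a signal or hide one.

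**Working it through.** **The plan's own figure.** The protocol gives no figure for censoring or for the resulting bias. Its example for a 365-day outcome is arrhythmia at 0.02 events per person (Table 2). The Poisson formula n = (z₀.₉₇₅ + z₀.₈₀)² (λ₀ + λ₁)/(λ₁ − λ₀)² with λ₀ = 0.02 and λ₁ = 0.04 gives 7.849 × 0.06/0.0004 = 1,177.3, rounded up to 1,178, as printed. That figure is not in dispute. The mean rate of 0.02 is used below.

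**Mechanism.** Let a covariate stratum have a constant censoring hazard, let x be hazard × interval length, and let S = e^(−x) be the probability of staying uncensored to the end. As a share of full follow-up:

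- unweighted person-time is (1 − S)/x, to first order 1 − x/2;
- with the written weight 1/S it is (1 − S)/(xS), to first order 1 + x/2;
- with the weight for each day it is 1.

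A shortfall of x/2 becomes an excess of x/2. The stabilising numerator is constant within a cohort and cancels from the rate.

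**Worked case.** These inputs are assumptions, not in the protocol: two equal strata with rates 0.01 and 0.03 per year (mean 0.02); comparators censored 40% and 10% (25% overall); no such censoring in the vaccinated cohort; true IRR 1.

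Even censoring: x = −ln 0.6 = 0.511 and −ln 0.9 = 0.105.

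- Person-time: 0.4/0.511 = 0.783 and 0.1/0.105 = 0.949.
- Unweighted comparator rate: (0.01 × 0.783 + 0.03 × 0.949)/(0.783 + 0.949) = 0.02096. IRR = 0.02/0.02096 = 0.954.
- Written weight: 0.783/0.6 = 1.305 and 0.949/0.9 = 1.055. Rate = (0.01305 + 0.03164)/2.360 = 0.01894. IRR = 1.056.

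If all censoring falls in the first three months, person-time is 0.25 × 0.783 + 0.75 × 0.6 = 0.646 and 0.25 × 0.949 + 0.75 × 0.9 = 0.912. If it all falls in the last three, it is 0.75 + 0.25 × 0.783 = 0.946 and 0.75 + 0.25 × 0.949 = 0.987. Weighting again by 1/0.6 and 1/0.9 gives:

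| Who leaves more | Timing | IRR, no censoring weight | IRR, written weight |
|---|---|---|---|
| Low risk | Even | 0.954 | 1.056 |
| Low risk | First 3 months | 0.921 | 1.015 |
| Low risk | Last 3 months | 0.989 | 1.098 |
| High risk | Even | 1.050 | 0.950 |
| High risk | First 3 months | 1.093 | 0.985 |
| High risk | Last 3 months | 1.011 | 0.918 |

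The sign reverses in every row. The size does not always grow: early censoring leaves a smaller bias than no weight, late censoring a much larger one. With 70% of the censoring hazard early and 30% late (low-risk leaving), 0.940 becomes 1.038.

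**Capping and the correct weight.** A simulation of the 40%/10% case with 4 million per cohort and the percentile cap gave 0.947 without weighting and 1.048 with the written weight. Interval-specific weights gave 0.99 to 1.00 at a true IRR of 1, and 1.98 to 2.01 at a true IRR of 2, across all timings and both directions.

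**The imbalance rule.** With weights 1/0.6 and 1/0.9 the low-risk share of comparators becomes 1.667/2.778 = 60%, against 50% in the vaccinated. The standardised difference is 0.10/√((0.24 + 0.25)/2) = 20%, so the covariate enters the model and most of the bias goes. In a simulation with 12 frailty markers and 41% of comparators censored, no marker crossed 10%. The IRR was 0.954 unweighted, 1.060 as written (after the cap) and 0.998 with interval-specific weights.

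**Scale against sampling error.** At 1,178 per cohort and 0.02 events each, the standard error of the log IRR is √(2/23.6) = 0.29, and a log bias of ln 1.056 = 0.054 is lost in it. At 426,570 per cohort (a Table 2 size for Guillain-Barré syndrome) it is √(2/8,531) = 0.015, and the same bias is about 3.6 standard errors. Both ignore the loss of precision from weighting.

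**The case against.** The strongest reply is that the worked case stops before the plan does. The 10% rule would fire at 20% imbalance, and adjusting for the stratum removes that bias. This stands: the two-stratum figures show the weight's own effect, not necessarily the reported IRR. What survives is risk spread over many covariates. Even there, a composite could trigger adjustment: in a similar 12-marker check with about 43% censored, the sum of the markers had a standardised difference of 13% to 30%. But the Charlson composite and a frailty index are optional in section 9.3.3, so the rescue is incidental.

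A reader might infer that the error always pushes towards false harm. The documents do not support that. It requires later-vaccinated comparators to be at lower risk, and the protocol does not say so. Nor can the new bias be said always to match or exceed the old one: vaccination is seasonal, the protocol gives no timing, and early censoring leaves a smaller bias.

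The weighting is also conditional, and most Table 1 windows are 42 days or less, where the trigger is less likely. Negative controls and quantitative bias analysis (section 9.7.4) might detect residual bias but would not correct the weight.

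Section 9.7 leaves detail to the SAP and lets it modify the plan. That covers interval length and time-updated covariates. It does not make a formula already written out in the protocol correct.

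Reading the formula as weighting only people with C=0 does not help. Events before censoring would stay while censored event-free time is dropped; simulated IRRs at a true value of 1 were then 0.69 to 0.97.

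**Conclusion.** The point holds in limited form. The stated weight does not suit the person-time it multiplies, and when triggered it reverses the sign of the censoring bias. Under the assumed 40%/10% censoring and threefold risk difference, the IRR at a true value of 1 shifts by about 2% (early), 6% (even) or 10% (late) one way, and by similar amounts the other way if high-risk comparators leave more. These are sizes before the imbalance rule, which removes most of the bias when the responsible covariates exceed 10% and little when none does. The exposure is mainly in the 365-day cohort-only outcomes, and it matters most when cohorts are large enough for a shift of a few per cent to exceed sampling error.

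A lesser point also stands: section 9.7.3.1 does not say which causes count as censored in C, while the list in section 9.7.2 puts death and end of data beside RSV vaccination.

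**What to change.** In section 9.7.3.1, replace the formula with cumulative, stabilised, interval-specific weights: for each interval of follow-up, the inverse probability of being uncensored up to that interval, applied to that interval's events and person-time, with follow-up split accordingly. State which causes of censoring the weight models, namely RSV vaccination and loss to follow-up. Assess baseline balance on the ATT weight alone. Make these changes together: moving the balance check while keeping the present formula would remove the step that now sometimes repairs it.

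The cost is protocol wording, a person-period data set and some extra programming in the common R scripts, before comparative analysis. No new data are needed. Interval length, updating covariates during follow-up and handling death as a competing event are optional details for the SAP.

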Baseline demographics and clinical characteristics for ABRYSVO vaccinated and unvaccinated individuals will be summarized using descriptive statistics. Descriptive statistics will also be used to summarize ABRYSVO uptake characteristics. Incidence rates per 1,000 patient years (and corresponding 95% CIs) will be calculated for all outcomes of interest in the ARBYSVO vaccinated and unvaccinated cohorts separately.

For the comparative cohort design, outcome specific incidence rates in the ABRYSVO vaccinated cohort will be compared to incidence rates in the unvaccinated cohort. Average treatment effect for the treated (ATT) weighting based on the propensity scores (PS) will be used to ensure baseline comparability between the vaccinated and unvaccinated cohorts. Stabilized inverse probability of censoring weighting (IPCW) will also be used if informative censoring between the cohorts is observed. After weighting, the distribution of baseline characteristics will be evaluated between the vaccinated cohort and the unvaccinated cohort, and variables that are inadequately balanced (standardized difference >10%) between the two cohorts will be included as regression model covariates in a doubly robust approach. Weighted Poisson regression models will be conducted, and incidence rate ratios and corresponding 95% confidence intervals (CIs) will be summarized.

For the SCRI design, the study population will include individuals who have received ABRYSVO, and experienced the specific outcomes of interest during the post-vaccination risk or control interval. Individuals who experienced a prespecified outcome following ABRYSVO vaccination serve as their own control by comparing the incidence of the outcome in the post-vaccination risk interval to the incidence of the outcome in a post-vaccination control interval using a conditional Poisson regression model. From this model, incidence rate ratios and 95% CIs will be reported.

Meta-analysis: Using the main estimates from each data source, appropriate random-effects meta-analytic methods may be used to obtain a combined effect estimate within each population of interest for both the comparative cohort and SCRI design analyses.

Milestones

• Protocol submission: on or before 31 March 2024

PFIZER CONFIDENTIAL

CT24-WI-GL02-RF02 5.0 Non-Interventional Study Protocol Template For Secondary Data Collection Study 01-Aug-2023 Page 15 of 72

- Progress report: 30 September 2025 (or 12 months after protocol endorsement by EMA)

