9.1.1. Primary Design - Comparative Cohort Design

A comparative cohort design will be used to estimate incidence rates and incidence rate ratios of prespecified outcomes among immunocompromised, or renally impaired, or hepatically impaired older adults with and without receipt of the ABRYSVO vaccine. Individuals in the unvaccinated cohort must have no record of an RSV vaccine on the index date or in the baseline period prior to index date or any other vaccine on the index date but can later receive ABRYSVO and enter the vaccinated cohort if all eligibility criteria are met. To address possible selection bias due to health seeking behaviours, unvaccinated individuals will be randomly selected from a population of patients who have regular use of preventive medical care, defined as at least one vaccination record in the year prior to the index date. The baseline period is defined as 12 months prior to the index date. The follow-up period will begin from day 1 (the day after ABRYSVO administration for vaccinated cohort, or the day after matched index date for the unvaccinated cohort) and continue to the earliest occurrence of an outcome, date of RSV vaccination (for unvaccinated individuals who later receive any RSV vaccine only), the end of administrative follow-up, end of the study period, or death. For those outcomes with a defined risk window, follow-up will also be truncated at the end of the risk window. To enhance comparability between the vaccinated and unvaccinated cohorts, ATT weights will be used. Weights, based on PS, will incorporate additional measures of healthcare utilization in the baseline period to further account for potential differences in healthcare seeking behaviour between the vaccinated and unvaccinated cohorts. However, as this study focuses on patients with chronically managed conditions, differences in healthcare seeking behaviour are not anticipated. IPCW will also be employed if informative censoring (i.e., differential rates of censoring during follow up) and high censoring rates are observed between the vaccinated and unvaccinated cohorts. Examples of patient follow-up scenarios are depicted in Figure 1 and Figure 2. Comparative analyses will also include variables that remain inadequately balanced between the two cohorts in a doubly robust approach. Further details are provided in Section 9.7.2 and Section 9.7.3.

Figure 1 Comparative Cohort Design

[figure not shown]

Notes:

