9.7.1. Baseline Characteristics

Baseline demographics and clinical characteristics for individuals vaccinated with ABRYSVO and the unvaccinated cohort will be summarized using descriptive statistics, consisting of the mean, SD, median, inter-quartile range, minimum, and maximum values for continuous variables and frequency distributions for categorical variables. Descriptive statistics will also be used to summarize ABRYSVO uptake characteristics, including calendar year and month of vaccination and care setting of vaccination (e.g., outpatient clinic, pharmacy, inpatient ward if available).For the comparative cohort design analysis, crude standardized differences in the baseline characteristics will be calculated between vaccinated and unvaccinated cohorts before and after weighting. Standardized differences <10% will indicate that the baseline characteristics of ABRYSVO vaccinated and unvaccinated cohorts are balanced.

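### The cohort analysis is called doubly robust, but only covariates left more than 10% imbalanced enter the outcome model, so when balance checks pass the IRR rests on the weights alone

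*Protocol*

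**What the plan says.** Section 9.7.3.1 weights the unvaccinated to resemble the vaccinated: "ATT weights will be PS/(1-PS) for individuals with no record of ABRYSVO", with weight one for the vaccinated. The weights are multiplied by censoring weights if informative censoring is found, and "extreme weights will be truncated or capped at the 1st and 99th percentile". Balance is then examined, and "variables that remain inadequately balanced (standardized difference >10%) between the two cohorts will be included as regression model covariates in a doubly robust approach". Effects come from this step: "Weighted Poisson regression models will be conducted to calculate IRRs of outcomes among vaccinated cohort vs. unvaccinated cohort".

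The abstract repeats the rule ("variables that are inadequately balanced (standardized difference >10%) between the two cohorts will be included as regression model covariates in a doubly robust approach"), and so does section 9.1.1 ("Comparative analyses will also include variables that remain inadequately balanced between the two cohorts in a doubly robust approach"). Section 9.7.1 sets the pass mark: "Standardized differences <10% will indicate that the baseline characteristics of ABRYSVO vaccinated and unvaccinated cohorts are balanced". No section places a fixed or full set of confounders in the Poisson model.

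**The concern.** Double robustness means that the estimate is consistent if either of two models is correct: the one for vaccination or the one for the outcome. The second model protects only if it could be correct by itself, so it has to contain the confounders. Here a covariate enters only when weighting has visibly failed for it. If nothing fails, there is no second model. If one or two covariates fail, only those enter, and that is still not a confounder model.

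The check is also a poor guide to when a second model is needed. Each variable can look balanced while a joint or curved effect missed by the propensity model remains unbalanced.

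The cohort is the primary design. In Table 1, arrhythmia, heart failure, coronary artery disease and death are assigned to the cohort design only. Readers of those IRRs would credit them with a protection against propensity-model error that the stated rule does not give.

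**Working it through.** The plan gives no figure for this point, and the sample sizes in Table 2 do not bear on it. Three checks follow. All confounder prevalences and strengths are assumptions; the 10% limit, the ATT weights and the percentile capping are the protocol's.

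**1. Imbalance that the rule leaves unadjusted.** Take a binary confounder present in 20% of one cohort and 24.14% of the other after weighting.

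- Standardized difference = (0.2414 − 0.20) / √[(0.2414×0.7586 + 0.20×0.80)/2] = 0.0414/0.4142 = just under 0.10, so it passes and is not adjusted.
- Bias factor in the IRR = [1 + (RR−1)×0.2414] / [1 + (RR−1)×0.20].
- Confounder RR 2: 1.2414/1.20 = 1.034.
- Confounder RR 3: 1.4828/1.40 = 1.059.

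At RR 1.5, with prevalence 0.1 to 0.5, the factor is 1.01 to 1.02. Five independent confounders, all just under the limit and all in one direction (prevalence 0.2), would give 1.09 at RR 1.5 or 1.18 at RR 2. That is an extreme case.

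**2. Balance passes while the propensity model is wrong.** Take two independent binary confounders x and w, each with prevalence 0.4.

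- Vaccination log-odds: −1.2 + 0.3x + 0.3w + 1.0xw.
- Event rate: 0.02·exp(0.3x + 0.3w + 1.0xw). Vaccination has no effect (true IRR 1).
- The propensity model omits xw. There is no capping.

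| x,w | Share | True P(vaccinated) | Fitted P | Rate |
|---|---|---|---|---|
| 0,0 | 0.36 | 0.2315 | 0.1970 | 0.0200 |
| 1,0 | 0.24 | 0.2891 | 0.3407 | 0.0270 |
| 0,1 | 0.24 | 0.2891 | 0.3407 | 0.0270 |
| 1,1 | 0.16 | 0.5987 | 0.5212 | 0.0991 |

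- Vaccinated rate = Σ share·P·rate / Σ share·P = 0.01490/0.3179 = 0.0469.
- Weighted unvaccinated rate, with weight = fitted P/(1 − fitted P): Σ share·(1−P)·weight·rate / Σ share·(1−P)·weight = 0.01304/0.3141 = 0.0415.
- IRR = 0.0469/0.0415 = 1.13.
- x and w each stand at 52.0% against 50.3%, a standardized difference of 0.033. Both pass, so no covariate enters.
- The joint category x = w = 1 stands at 0.0958/0.3179 = 30.1% against 0.0699/0.3141 = 22.2%.

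Simulation (40 runs of 200,000) agrees: 1.133 under the protocol's rule, and 1.004 with the same weights and a correct outcome model. With a correct propensity model both give 1.001. The Monte Carlo standard error is about 0.004 on the log scale.

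**3. With the protocol's capping.** One normal and one binary covariate, true IRR 1, unvaccinated weights capped at the 1st and 99th percentiles, runs of 400,000. All standardized differences were below 7%.

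| Assumed log-effects | Propensity model | IRR, protocol rule | IRR, same covariates kept as main effects |
|---|---|---|---|
| 0.2-0.3 | product term omitted | 1.03-1.06 | 1.02 |
| 0.5 | product term omitted | 1.26 | 1.06 |
| 0.5 | correct | 1.15 | 1.03 |

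A repeat with binary prevalence 0.4, vaccination intercept −1 and base rate 0.02 agreed to within 0.02. The last row shows that part of the bias comes from capping, not from the missing product term.

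**The case against.** **It is mainly a matter of labelling.** ATT weighting followed by adjustment for what remains imbalanced is a recognised practice that reduces bias. Deleting the term would correct the document without changing an estimate. This stands as a defence of the method, but not of the claimed property. The checks also show that keeping the covariates in the model lowers bias at little cost, so more than the label can be improved.

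**The propensity model is not fixed.** Section 9.7.3.1 says only that it is logistic and what it may include. Interactions and non-linear terms are not ruled out, and a product term listed as its own variable would be caught by the balance check. This stands. It limits what can be said about size, but a richer propensity model is still one safeguard, not two.

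**One rule must serve many outcomes.** They include GBS at 6 to 10 per 100,000 person-years, in three populations and five data sources. A full outcome model may not be estimable for the rare ones. This stands and shapes the fix.

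**Other checks exist.** Section 9.7.4 lists negative controls, quantitative bias analysis and a possible SCRI for atrial fibrillation and supraventricular arrhythmias, and section 9.9 acknowledges residual confounding. These help, but they are worded as conditional. Section 9.9 attributes residual confounding to variables that are not captured or have missing values, not to an error in the propensity model.

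**A stronger reading.** A reader might infer that the primary IRRs will be biased by 20% or more. The documents do not support this: it takes strong assumed confounding together with a misspecified propensity model, and capping accounts for part of it. A reader might also infer that a short list of main effects would earn the label. It would not: bias fell from 1.26 to 1.06, not to 1.00.

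**Conclusion.** The point holds as a mismatch between the stated rule and the property claimed for it in the abstract, section 9.1.1 and section 9.7.3.1. When all covariates pass the 10% check, the IRR depends on the propensity weights, and any censoring weights, alone.

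The consequence is probably small to moderate: 3-6% for a single confounder just under the threshold at rate ratio 2 to 3, and a similar amount from a missed joint effect of moderate strength. These sizes rest on assumed prevalences and effects, since the protocol gives none. With an adequate propensity model and little effect of capping, the bias is negligible. The analysis is not invalid, but it has less protection than it claims.

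**What to change.** Change the text in section 9.7.3.1, section 9.1.1 and the abstract along these lines:

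- **Outcomes with enough events:** the weighted Poisson model includes the prespecified main confounders (those used in the propensity model, as far as event counts allow) whatever their standardized difference after weighting. The SAP sets the event-count criterion and the order in which terms are dropped.
- **Rare outcomes:** keep the present rule, described as ATT weighting with adjustment for residual imbalance.
- **Label:** use 'doubly robust' only where the outcome model carries the full confounder set. Use the plainer description everywhere else.

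The cost is wording in three places, matching SAP text and a slightly larger model for common outcomes. With a log link the IRR keeps its meaning if the vaccine effect is homogeneous. If it is not, predictions can be standardised to the vaccinated cohort to retain the ATT. If only the minimum is done, correcting the label changes no estimate.
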